1.5 Does Scrambler Therapy Actually Work?

Arguments against Scrambler therapy certainly exist, with critics attributing much of the benefit to a placebo effect. Some of the positive endorsements in social media and on the internet are only anecdotal. Additionally, the developer of Scrambler therapy participated in the initial clinical trials, and this could be perceived as a potential conflict of interest even though it is scientifically desirable and logical to expect that the same person who invented this therapy, would be one to report the results. Additionally, there are no large, placebo-controlled, double-blinded clinical trials to estimate the effectiveness of Scrambler therapy.

On the other hand, while some reports (Marineo 2003; Sabato, Marineo et al. 2005; Marineo, Iorno et al. 2011; Coyne, Wan et al. 2013) involved the inventor of the Scrambler device, these positive findings have been independently replicated by diverse groups (Smith, Coyne et al. 2010; Abdi, Lakkimsetty et al. 2011; Ghatak, Nandi et al. 2011; Ricci, Pirotti et al. 2011; Sparadeo F 2012; Campbell, Nimunkar et al. 2013; Coyne, Wan et al. 2013; Park, Sin et al. 2013; Moon, Kurihara et al. 2014; Pachman, Weisbrod et al. 2014; Sparadeo and D'Amato 2014; Starkweather, Coyne et al. 2015) in nearly all of the reported studies, involving over 700 patients in total. In some cases, the benefit achieved has been substantial, with some patients achieving complete pain resolution and substantially reduced dependence on pharmacologic therapy. There has been only one report of a negative experience¹ (Campbell, Nimunkar et al. 2013). This was from one small, placebo-controlled trial in patients with chemotherapy-induced peripheral neuropathy. This was published only as an abstract, did not show much of a reduction in either study arm (arguing against a placebo effect), and it is worth noting that

the group did not have much experience using Scrambler therapy prior to conducting this trial. This raises concerns regarding the validity of this trial as data have demonstrated an extended learning curve with the provision of Scrambler therapy, particularly for chemotherapy-induced neuropathy (Pachman, Weisbrod et al. 2014).

1.6 Additional Research is Needed

Additional work is needed to better understand the mechanism of Scrambler therapy and to conduct larger randomized clinical trials investigating the efficacy of Scrambler therapy in a number of chronic pain states. Randomized, sham-controlled double-blinded trials, involving patients with a variety of chronic pain syndromes, would strengthen the conclusions from initial studies. The data compiled, to date, support the feasibility and value of such an undertaking. However, there is significant controversy amongst those who treat patients with Scrambler therapy as to whether a blinded placebo control is realistic. Part of the process of correct treatment is placing the electrodes properly and getting feedback from the patient that the pain has been markedly improved. If that is not achieved, the leads should be reapplied in a different area and the process repeated until there is success in replacing the patient's perception of pain with the characteristic pleasant sensation from the Scrambler's electric stimuli, and markedly improving the initial pain. It is, thus, argued by some that the nature of the treatment technique makes placebo control impractical, just as in certain surgical procedures (e.g. laparoscopic versus open colectomy(2004). Thus, it could be argued that trials should be randomized and compared to other potential treatments, rather than a placebo. An example of such a trial was discussed above where Scrambler therapy was compared to guideline-based drug therapy (Marineo, Iorno et al. 2011).

The possibility of variability in treatment outcomes being attributed to differences in how and where electrodes are applied suggest that the next phase of research more objectively evaluate fidelity to intervention in terms of electrode placement over repeated sessions. We suspect that there is a group learning phenomenon in how electrodes are placed serially, such that teams delivering the intervention may get better at delivering the intervention over time. In order for larger scale trials with more heterogeneous teams to eventually implement a trial of scrambler therapy, we need to gather more information about fidelity to the intervention through direct observation with video technology.

1.7 Rationale for using TENS as a control

TENS (Transcutaneous electrical nerve stimulation) therapy, first developed in 1974, has been utilized for treatment of neuropathic pain from a variety of causes.

TENS is commonly done using a small unit, operated by a battery, with 2-4 leads that can be applied to the skin via sticky attachment pads. They are usually available for patients to use at home, following some relatively simple instructions.

A few small studies have explored TENS units for treatment of diabetic neuropathy. Whereas these small studies have not demonstrated convincing evidence of benefit on their own, a meta-analysis suggests that TENS may provide some benefit for diabetic neuropathy.(Jin, Xu et al. 2010; Pieber, Herceg et al. 2010) Nonetheless, it is generally agreed that larger, placebo-controlled clinical trials are necessary to delineate whether TENS is helpful for diabetic neuropathy.

To our knowledge, there are no good studies available looking at TENS therapy for treatment of chemotherapy-induced peripheral neuropathy.

There are potential pros and cons for evaluating TENS as a sham control. The advantages are that it has similarities to the Scrambler machine. For example, wires are placed on the skin in a similar manner and an electrostimulation sensation is felt by patients in a similar manner. The major disadvantage of using TENS as a control is that it, potentially, may actually help chemotherapy-induced peripheral neuropathy.

1.8 mRNA Information

Starkweather et al described mRNA gene expression changes in patients who received real versus sham Scrambler therapy. Starkweather et al treated 15 patients with real ST and 15 with sham ST for persistent low back pain, and observed in the ST group a significant downregulation in the serum mRNAs for 17 pain genes such BDKRB1 and NGF at the 3 week mark, many of which code for proteins and receptors that mediate inflammation and nociceptive signaling. (Table 1.71) (Starkweather, Coyne et al. 2015). We will also obtain a white blood count (WBC) collected as CBC with differential, as this count will help to illustrate that there were reasonable numbers of WBCs to obtain the RNA for testing.

Table 1.71. Differential Gene Expression in the Calmare Group at 3 Weeks Post-Treatment

Gene	Fold Regulation^a	p value
BDKRB1	-2.468	0.0069
CACNA1B	-1.518	0.0091
CHRNA4	-1.924	0.0053
GDNF -2.141	-2.141	0.0036
GRM1 -1.715	-1.715	0.0033
NGF	-2.599	0.0040
NTRK1	-1.980	0.0035
OPRD1	-1.812	0.0049

Brain system adaptations in responders (greater than 50% pain or tingling reduction) vs. non-responders data will be provided from this work.

1.9b Sensation Changes

Our clinical experience with patients receiving Scrambler therapy has supported that patients develop improved normal sensation in areas treated with Scrambler therapy. This includes improved feeling and proprioception. Thus, we plan to look at quantitative sensory testing (QST) in a subset of patients on this trial. [name] and colleagues at Mayo have world-renowned expertise in this area. We will, in an exploratory manner, obtain touch pressure and heat pain testing on both the dorsal foot and the lateral leg in 10 patients per study arm, before Scrambler/TENS therapy and on the last couple days of ScramblerTENS therapy.

1.9c Audiovisual recording rationale

As Scrambler therapy is operator dependent and there is a learning curve with providing it, obtaining audiovisual recording of the treatment sessions should be helpful. This recording may allow us to ask for outside input for individual treatments that are being performed. It may also allow us to provide examples of successful treatment of individual patients. Of course, patient confidentiality issues need to be kept in mind.

We are proposing to include video recording of intervention delivery into the routine delivery of the intervention. Using established direction/observation protocols developed with local clinical communication research experts, we will consent patients to be video recorded.

[name], a co-investigator on this protocol, has extensive expertise with regard to patient communication topics, which have included audiovisual recording sessions of patient encounters. After the trial is completed this recordings may be used to conduct a structured "fidelity to treatment" analysis in which two independent raters score the recorded intervention delivery for fidelity to protocol a priori criteria based on scientific expert criteria. If we do this, raters will be blind to the final clinical outcomes of participants, although they would hear patients' thoughts while they were getting the treatments.

2.0 Goals

2.1 Goal 1 Efficacy

Evaluate the efficacy of Scrambler therapy compared to TENS therapy for pain and/or tingling related to CIPN.

Hypothesis 1: Scrambler therapy will improve pain related to chemotherapy induced neuropathy more than TENS therapy.

2.2 Goal 2 Tolerability

Evaluate the tolerability of Scrambler therapy and compare it to TENS therapy, in this population.

Hypothesis 2: Scrambler therapy will be well tolerated and there will be no substantial differences in side effects between the Scrambler and TENS treatment groups.

2.3 Goal 3 Efficacy

Evaluate whether Scrambler therapy, compared to TENS therapy, can decrease the use of pain medication for CIPN.

Hypothesis 3: Pain medication and morphine oral equivalent dose (MOED) daily amounts will decrease more in the group receiving Scrambler therapy, compared to those who received TENS therapy.

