- 3.23 Existing implantable medical electronic devices, life-supporting medical devices, and medical monitoring devices.
Note: Metal implants for orthopedic repair, e.g. pins, clips, plates, cages, joint replacements are allowed, as are central venous access devices.
- 3.24 History of myocardial infarction or ischemic heart disease within the past six months.
- 3.25 History of epilepsy, brain damage, use of anticonvulsants for seizure prevention, concurrently using ketamine, symptomatic brain metastases.
- 3.26 Skin conditions such as open sores that would prevent proper application of the electrodes.
- 3.27 Other medical or other condition(s) that in the opinion of the investigators might compromise the objectives of the study.
- 3.28 Currently receiving gabapentin or pregabalin and not willing to be weaned off of these medications prior to Scrambler therapy initiation.
Note: It is OK to continue these medications in patients who are receiving TENS. (See [Appendix I](#)).
- 3.29a History of peripheral neuropathy prior to receiving neurotoxic chemotherapy.
- 3.29b Prior treatment with Scrambler therapy.

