4.0 Test Schedule

Use for first treatment period; repeat for second treatment period

Tests and procedures	Active Monitoring Phase				
	≤30 days prior to registration	Day 1, Prior to therapy	Daily for 14 consecutive days beginning on Day 1 of active therapy	Last day of assigned therapy (±1 day)	Weekly for 8 weeks
History and exam, PS ¹ , Eligibility questions ² (Appendix II: A or B)	X				
Pregnancy test ³		X			
Declaration of most problematic site (upper versus lower extremities) and most problematic symptom (tingling versus pain): Appendix III	X				
Pain/tingling questionnaire regarding the prior week (Appendix IV: A or B)		X ⁴			
Patient Questionnaire: Before each treatment (Appendix V: A or B)		X ⁵	X ⁵		
Patient Questionnaire: After each treatment (Appendix VI: A or B)			X ⁵		
EORTC CIPN 20 (Appendix VII)		X		X ⁶	X
Patient Questionnaire: Analgesic Use (Appendix VIII)		X	X		X
Patient Questionnaire After each therapy and during weekly follow-up: Global Impression of Change and Patient Preference (Appendix IX: A or B)			X ⁷		X ⁷
Daily Treatment Log and Adverse Assessment (Appendix X)			X		
Individual Patient Dermatome Map-Electrode Placement (Appendix XI) Scrambler only			X		
Audiovisual recordings ^R			X ⁸		
Weekly follow-up patient questionnaire (Appendix XII:A or B)					X ⁹
Written patient summary (if the patient is willing to provide) ^R					X ¹⁰
Research Blood draw for CBC/diff and mRNA ^{11,R}		X		X	
fMRI ^{12,R}		X		X	
Quantitative Sensory Testing ^{13,R}		X		X	

Tests and procedures	Active Monitoring Phase				
	≤30 days prior to registration	Day 1, Prior to therapy	Daily for 14 consecutive days beginning on Day 1 of active therapy	Last day of assigned therapy (±1 day)	Weekly for 8 weeks
Study Coordinator/Nurse phone call to discuss therapy and any concerns, record any adverse events that are reported and to remind the patient to complete questionnaires and mail them			X ¹⁴		X

Footnotes:

1. PS must be done ≤7 days prior to registration.
 2. Appendix II A or B, as labeled depending on neuropathy area type. (This evaluation is used for eligibility.)
 3. For women of childbearing potential only. Must be done prior to first Scrambler therapy (or the first day of the second treatment period, if Scrambler therapy is crossover).
NOTE: This testing is not needed for TENS therapy.
 4. Appendix IV A or B, as labeled depending on neuropathy area to be treated

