9.3 Other pain treatment

Other pain treatments are allowed if the pain is not satisfactorily controlled. All pain treatments and pain-related medications will be recorded.

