16.32 Secondary efficacy endpoints

Perceived treatment efficacy from the Subjective Global Impression of Change instrument (Appendix IXA and B) will be summarized (median and range for impression of change and frequency for preference) by arm and compared

(Wicoxon rank-sum test for impression of change and Chi-square test for preference) between treatment arms.

EORTC CIPN20 scores and changes in scores will be summarized (mean, sd, median, range) at each time point by arm and will be compared between arms using two-sample t-tests.

- 16.33 Goal: Evaluate the tolerability of Scrambler therapy and compare it to TENS therapy, in this population.

Frequency and type of toxicities occurred during therapy will be summarized by treatment arm and compared between arms using Fisher-exact test.

- 16.34 Goal: Evaluate whether Scrambler therapy, compared to TENS therapy, can decrease the use of pain medication for CIPN.

Type and frequency of analgesic used will be summarized by treatment arms and will be compared using Fisher-exact test.

- 16.35 Goal: Explore whether mRNA gene expression changes are similar to that previously reported by Starkweather et al.

In a descriptive manner, the gene expression will be compared to what was previously reported.

- 16.36 Goal: Explore whether Scrambler therapy will change fMRI.

Changes in fMRI following Scrambler therapy will be described in the subset of patients selected for this component of the study.

- 16.37 Descriptive statistics will be used for the data from Quantitative Sensory Testing.

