Appendix VIII Patient Analgesic Use Questionnaire

Initials _____
Study # _____
Date _____
Day _____

Please list all pain medications (drug, dose, and quantity) used in the past 24 hours.

Drug	Unit Dose	Quantity over past 24 hours
Example Acetaminophen or Tylenol	500 mg	4 pills

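### Goal 3 is about pain medication for CIPN, but the analgesic form shown does not ask what each drug is for, so drugs taken for other pain attenuate the comparison

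*Combined protocol and SAP*

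**What the plan says.** The objective in section 2.3, repeated in 16.34, is specific to an indication: "Evaluate whether Scrambler therapy, compared to TENS therapy, can decrease the use of pain medication for CIPN". Hypothesis 3, directly below it, drops that restriction: "Pain medication and morphine oral equivalent dose (MOED) daily amounts will decrease more in the group receiving Scrambler therapy".

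The form is Appendix VIII, which the test schedule (4.0) places on Day 1, daily during treatment and weekly in follow-up. Its instruction is "Please list all pain medications (drug, dose, and quantity) used in the past 24 hours". It has three columns: drug, unit dose and "Quantity over past 24 hours". None of them records indication or body site. Section 9.3 is equally general: "All pain treatments and pain-related medications will be recorded".

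The analysis in 16.34 reads "Type and frequency of analgesic used will be summarized by treatment arms and will be compared using Fisher-exact test". It gives no rule for picking out drugs taken for neuropathy.

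Eligibility does not specifically exclude other painful conditions or analgesics taken for them. The nearest criterion is 3.27, a general discretionary one: "Other medical or other condition(s) that in the opinion of the investigators might compromise the objectives of the study".

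One class of drug is handled differently by arm. Gabapentinoids must be stopped before and during Scrambler therapy (3.28, 9.2, Appendix I) but may be continued under TENS (note to 3.28).

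**The concern.** The goal, the form and the analysis describe different quantities. A treatment applied to hands or feet has no evident reason to change an analgesic taken for, say, joint or post-surgical pain. As written, such a drug counts the same as one taken for neuropathy. A patient who keeps taking it stays a user whatever the study treatment does, so the difference in use between arms shrinks.

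There may also be under-recording. Section 1.2 singles out duloxetine as the one agent with reasonable evidence of benefit in CIPN. A patient asked for pain medications may not think to list an antidepressant, and the form does not prompt for it.

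At stake is how a small difference on Goal 3 can be read. With these data, a weak effect on CIPN medication and a real effect masked by other analgesics would look alike.

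**Working it through.** **No figure to reproduce.** The documents state no rate, effect size or power for Goal 3. Table 16.51 concerns the primary endpoint only. What follows is an illustration with assumed rates.

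**Inputs**
- 25 patients per arm: section 16.5.
- Fisher's exact test: section 16.34. Two-sided 0.05 is assumed, since 16.34 gives no level.
- CIPN-drug use of 60% under TENS and 25% under Scrambler: assumed.
- q, the share of patients taking an analgesic for other pain: assumed 0% to 40%, equal in both arms and independent of CIPN-drug use.
- Endpoint, any analgesic v none: assumed. Section 16.34 speaks of type and frequency and does not define a pooled any-use variable.

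**Any-use comparison**

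P(any use) = 1 − (1 − p)(1 − q), with p the CIPN-drug use. The difference between arms is therefore (p_TENS − p_Scr)(1 − q).

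Example, q = 20%: TENS 1 − 0.40 × 0.80 = 0.68; Scrambler 1 − 0.75 × 0.80 = 0.40; difference 0.28 = 0.35 × 0.80.

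| q | TENS | Scrambler | Difference | Exact Fisher power |
|---|---|---|---|---|
| 0% | 60% | 25% | 35 points | 65% |
| 10% | 64% | 32.5% | 31.5 points | 55% |
| 20% | 68% | 40% | 28 points | 45% |
| 30% | 72% | 47.5% | 24.5 points | 35% |
| 40% | 76% | 55% | 21 points | 25% |

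With a smaller assumed effect, 60% v 30%, power goes from 51% to 42%, 33%, 25% and 19% over the same values of q.

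**Change in daily amounts**

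Hypothesis 3 speaks of a decrease in daily amounts. A drug for other pain taken at a constant dose drops out of each patient's change from baseline. Only variation over time in such drugs adds noise. Let r be the SD of change in other-pain use divided by the SD of change in CIPN use, with the two independent. The standardised effect d then becomes d / √(1 + r²). With d = 0.8 assumed and a two-sided 0.05 t-test at 25 per arm:

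| r | Effective d | Power |
|---|---|---|
| 0 | 0.80 | 79% |
| 0.25 | 0.78 | 77% |
| 0.5 | 0.72 | 70% |
| 0.75 | 0.64 | 60% |

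**Gabapentinoids**

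The calculations above cover only the contribution of other-pain drugs. They leave out the gabapentinoid rule, which lowers use in the Scrambler arm by protocol. That is a difference between arms that the device did not cause, and it acts on drugs likely to be labelled as taken for neuropathy.

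**The case against.** **The numbers are invented.** The rates, and the any-use endpoint, have no source in the documents. A comparison by drug type would not merge a neuropathic agent with a drug for joint pain as the model does. This stands: the tables show direction and a plausible range, not an estimate.

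**The goal may simply be loosely worded.** Hypothesis 3 omits the restriction to CIPN, so total analgesic use may be what was meant. In that case goal and hypothesis need reconciling in the text, and no form change is strictly required. This also stands, as a lesser remedy.

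**Stronger readings that a reader might infer, and that the documents do not support**
- *That the indication can never be recovered.* The On-Study form and the other case report forms listed in section 18 are not reproduced. Drug names and doses are recorded, and 9.3 extends recording to pain-related medications. The claim reaches only the forms shown.
- *That the comparison is otherwise unbiased and merely loses sensitivity.* The gabapentinoid rule already separates the arms by protocol.
- *That CIPN-indicated use should replace total use as the Goal 3 measure.* With gabapentinoids included, this would concentrate the protocol-imposed difference and could present a required wean as a Scrambler benefit.
- *That the loss for daily amounts is as large as for any use.* A fall from 79% to 50% needs r = 1, that is, other-pain use changing over time as much as CIPN use.
- *That this defect alone makes a null result uninformative.* Section 16.5 says the trial is sized on feasibility and is not confirmatory. Even the undiluted case above has only 65% power.

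**Conclusion.** The mismatch is real. Goal 3 names an indication that the analgesic form shown does not collect and that 16.34 does not isolate. Drugs for other pain attenuate a difference in use, by the factor 1−q in an any-use comparison. Under the assumed 60% v 25%, the cost is between 10 and 40 points of power for q between 10% and 40%. For change in daily amounts it is between 2 and 19 points for r between 0.25 and 0.75. The true size is unknown, because the documents do not give the share of patients with other pain.

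Severity is minor: Goal 3 is not the primary endpoint and carries no power claim.

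**What to change.** 1. Add a column to Appendix VIII: *Taken for your neuropathy? yes / no / both*, answered when a drug is first listed, so that its label does not shift as treatment proceeds.
2. Add a prompt asking patients to include antidepressants and other drugs taken for neuropathy.
3. In 16.34, report CIPN-indicated use beside total analgesic use, and state in advance how *both* is counted.
4. Report gabapentinoids separately and base the CIPN-indicated comparison on non-gabapentinoid drugs. State that the arm difference in gabapentinoid use follows from 3.28 and 9.2 and is not a treatment effect.
5. Align the wording of Goal 3 and Hypothesis 3. If the form is not changed, word the goal as total analgesic use.

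The cost is one column and one prompt on a one-page form, plus a few sentences in 16.34. The downside is that indication is self-reported by patients who know which device they are using. Fixing the label at first listing does not protect drugs first listed after treatment starts. Total use is kept alongside for that reason.
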